10.2 Off-Study Criteria and Survival Follow-Up

Patients will only be off study at the time of death. Patients will be followed every two months for progression, for up to one year from the off-treatment date. All patients will be followed for survival every 2 months for the first 2 years from the off-treatment date; after 2 years, patients will be followed every 6 months until death. Survival status may be obtained by phone call, clinic visit, or medical records (e.g. physician notes/laboratory results of clinic or hospital visit).

11.0 STATISTICAL CONSIDERATIONS

Phase I /Dose Finding

The primary objective of the phase I study is to determine the safety combination treatment of pamiparib (BGB-290) given at a fixed dose level of 60 mg BID with TMZ 20 mg starting at the dose level/schedule 1 (Days 1-28), then subsequently dose level -1 (Days 1-21), dose level -2 (Days 1-14), and dose level -3 (Days 1-7) in patients with recurrent gliomas and IDH1/2 mutations. The standard 3+3 design will be used for dose finding. Three patients will be treated in a dose/schedule cohort and dose deescalation/changing treatment schedule, if required will take a stepwise fashion with expansion to a total of 6 patients at a putative MTD/ or highest safe dose/schedule. The target DLT rate is 33%.

The MTD is defined as the combination regimen that yields a DLT rate less than, or equal to 33%.

The safety evaluation period is 28 days (the first cycle of treatment) for dose escalation decisions. All safety and toxicity will be followed and data will be collected till 90 days after discontinuation of the treatment.

NCI Common Terminology Criteria for Adverse Events (CTCAE) version 5.0 will be used for scoring toxicity and adverse events. The severity and frequency of toxicity will be tabulated by the tested doses using descriptive statistics. The proportions of subjects who experienced grade 3 or above toxicities will be estimated, along with 95% confidence intervals by each type of toxicity.

ABTC # 1801

NCI # ABTC-1801

PI: [name]

The Phase II efficacy study will be warranted after a safe combination regimen is deemed.

Phase II/ Safety and Efficacy

The primary objective of the phase II portion of the study is to estimate treatment effect in terms of tumor radiographic response in two different patient populations independently. One is a poor risk patient population, alkylator resistant/alkylatorrefractory: Arm A. The other is favorable risk patients who had one distant alkylator failure: Arm B.

Primary Endpoint:

The primary endpoint for both Arm A and B is tumor radiographic response (CR+PR) using Response Assessment in Neuro-Oncology (RANO) criteria by measurable disease.

Study Design /Sample Size:

Arm A: It is a single arm design to test a hypothesis of clinical benefit of 25% radiographic response rate (PR+CR) for patients who failed multiple prior alkylator therapies and are treated with BCB290+TMZ to compare a null of 5%. The sample size estimation is based on a 2-stage design (MiniMax). A total sample size of 25 patients yields 90% statistical power to detect 20% improvement from a null of 5% with a false positive rate at 5%. At the first stage, 15 patients will be enrolled onto the study. The trial will be stopped and the null hypothesis accepted if no response was obtained among the first 15 patients (0/15). Otherwise, the study will continue to stage 2. The probability of early stopping for futility is 0.46 when the null is true and 0.01 when a true response is 25%. Ten additional patients will be enrolled on the second stage of the trial. If 4 or more patients out of the 25 have objective response, the study will reject the null hypothesis to conclude that pamiparib (BGB-290) in combination with TMZ is effective to treat patients with recurrent, alkylator-refractory, and IDH1/2-mutant glioma.

Arm B: It is a single arm study to test a hypothesis of clinical benefit of 50% radiographic response rate (PR+CR) for patients who failed one prior alkylator therapy and are treated with BCB290+TMZ to compare a null of 30%. The sample size estimation is based on a 2-stage design (MiniMax). A total sample size of 53 patients yields 90% statistical power to detect a 20% improvement from a null of 30% with a false positive rate at 5%. At the first stage, 24 patients will be enrolled onto the study. The trial will be stopped and accept the null hypothesis if 7 or fewer responses were obtained among the first 24 patients (\leq 7/24). Otherwise, the study will continue to stage 2. The probability of early stopping for futility is 0.57 when the null is true and 0.03 when a true response is 50%. Twenty-nine additional patients will be enrolled in the second stage of the trial. If 22 or more patients out of the 53 have objective responses, the study will reject the null hypothesis to conclude that pamiparib (BGB-290) in combination with TMZ is effective to treat patients with recurrent, IDH1/2-mutant glioma who failed initial alkylator therapy.

ABTC # 1801

NCI # ABTC-1801

PI: [name]

Additional considerations on first stage/interim analysis:

Arm B (Low risk patients): the study will consider that a 60% of patients with the tumor growth rate reduction $\geq 50\%$ is clinical meaningful to compare with a null of 30%. A total of 24 patients in the interim analysis per primary design will have a statistical power of 89% to detect 30% difference at a target significance level of 0.05 (1-sided). It requires 12 or more patients out of the 24 to achieve tumor growth rate reduction on FLAIR of 6-month \geq 50%.

The definition of response for the primary endpoint will follow the response criteria (section $\underline{8.0}$) with a confirmatory MRI scan at least 4 weeks apart from the initial scan of response. Probability of responses will be estimated using binomial distribution along with 95% confidence interval. Arm A and B will be evaluated independently.

ABTC # 1801

NCI # ABTC-1801

PI: [name]

Secondary Endpoints:

- Progression-free survival: the progression-free survival time is defined as the time from a date of treatment start to a date of the initial scan deemed tumor progression while patient is alive. The data will be censored if progressive disease was not observed at the time of data cut-off for analysis. Progression-free survival (PFS) and median PFS will be estimated using Kaplan-Meier method along with 95% confidence interval.
- Overall survival: survival time is defined as the time from a date of treatment started to a date of death. The data will be censored if patient was alive at the time of data cut-off for analysis. Overall survival (OS) and median OS will be estimated using Kaplan-Meier method along with 95% confidence interval.
- Duration of the response (CR or PR): the duration of response is defined as the time from a date of initial scan of a response to a date of the initial scan deemed tumor progression. Results of the duration will be summarized using descriptive statistics.
- Safety/toxicity: adverse events per CTCAE (version 5.0). The proportion of patients with serious or life threatening toxicities will be estimated along with 95% confidence intervals.

Exploratory Objectives:

- 1. To assess tumor response rates, PFS, and OS in patients with WHO grade IV glioblastoma (GBM) treated with pamiparib (BGB-290) and TMZ. Ten grade IV recurrent IDH1/2 mutant GBM patients will be enrolled on to the GBM Arm to be treated with pamiparib (BGB-290)+TMZ using the combination doses defined in the phase I portion. The sample size is not based on a statistical considerations but clinical feasibility. The same tumor response criteria, definitions of OS and PFS for Arm A and B also apply in this GBM Arm. A tumor response rate will be estimated using binomial distribution (exact method) along with 95% confidence interval. Duration of tumor response, PFS and OS will be summarized and presented using standard methods.
- 2. To assess the mutational landscape via whole-exome sequencing (WES) using the tumor tissue obtained from previous surgical resection or biopsy. Particular interests of mutated gene including ATRX, CIC, FUBP1 and CDK4. Overall description of possible mutations will be summarized descriptively using descriptive statistics. Possible association between mutations and treatment effect will be explored using statistical molding approach based on type of treatment outcomes. False discovery rate will be provided for any discovery results.
- 3. To assess gene expression patterns using RNA sequencing (RNAseq). Overall description of possible gene expression patterns using RNA sequencing will be summarized descriptively using descriptive statistics. Possible association
ABTC # 1801

NCI # ABTC-1801

PI: [name]

between change in gene expression level and treatment effect will be explored using a statistical modeling approach based on type of treatment outcomes and patterns of change in gene expression. False discovery rate will be provided for any discovery outcomes.

- 4. To assess the methylation profiling with Infinium Methylation Assays, methylation status will be quantified as either methylated or unmethylated. Methylation status will summarized using descriptive statistics. Possible association with treatment outcomes can be assessed using regression modeling.
- 5. To quantify 2-hydroxyglutarate (2HG) in archival FFPE specimens via LC-MS detection and correlate with treatment response. The tumor tissues also will be used to quantify cellular metabolism marker (2HG) through Liquid Chromatography-mass Spectrometry. 2HG concentration will be measured as pmol/mg tissue. Output data will be normalized prior to analysis and data will be summarized using descriptive statistics such as mean, standard deviation, and quantiles etc. Regression model could be used to explore possible association with treatment outcomes such as stable disease versus progressive disease (primary clinical outcome per RANO) at a specific landmark time, or treatment responders (tumor response per RANO) versus non-responders, or progression-free survival and survival time etc. False discovery rate will be provided for any discovery results.
- 6. To explore possible association of 2HG levels, somatic alterations, gene expression / methylation patterns in FFPE tumor tissue, person correlation coefficient or spearman correlation coefficient could be used according to characteristics of the data.
- 7. PK: to assess tumor tissue pamiparib (BGB-290) levels, 2HG, and PARylation in a patient subset treated with drug prior to re-resection. Ten clinically indicated surgical candidates will be enrolled onto the surgical arm for drug concentration and tissue biomarkers study. The concentration of pamiparib (BGB-290) will be determined in a $0.05-0.10 \text{ cm}^3$ (50-100 mg) section of tumor tissue obtained from a contrast enhancing and non-contrast enhancing region of the tumor. Data will be normalized (e.g. taking logarithms) prior to analysis. Concentration levels of pamiparib (BGB-290), 2HG, and PARylation will be summarized using descriptive statistics independently. To characterize the steady state pharmacokinetics at a given dose and sampling time. Individual subject plasma concentration-time curves will be analyzed by non-compartmental methods using routines supplied in the WinNonlin Professional Version 5.0 software package (Pharsight Corp., Cary, NC). The geometric mean \pm standard deviation of the estimated values of the pharmacokinetic parameter for groups of subjects evaluated at the given dose level will be calculated. Pharmacokinetic parameters, such as C_{max}, C_{min}, and AUC etc will be summarized descriptively.

ABTC # 1801

NCI # ABTC-1801

PI: [name]

- 8. To evaluate changes in tumor growth rate of 6 months in subjects with nonenhancing glioma based on fluid attenuated inverse recovery (FLAIR) tumor volume measurements of serial MRI exams. The tumor growth rate of 6 months is defined as a percent change of FLAIR tumor volume with non-enhancing glioma during a 6-month period. The difference of tumor growth rate of 6 months prior to treatment and during/ after treatment will be analyzed using paired t-test.
- 9. To assess whether change in tumor growth rate (based on FLAIR tumor volume) in subjects with non-enhancing glioma before and after treatment is associated with progression by Response Assessment in Neuro-oncology for Low Grade Gliomas (RANO LGG; phase II patients only) or survival. Cox regression model will be used to assess such possible association adjusting for well-known clinical prognostic factors.

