4.3 Surgical Portion

Following completion of the Phase I portion, 10 patients with recurrent IDH1/2-mutant glioma (WHO grade II-IV) who are eligible for re-resection at the time of recurrence may be enrolled on a surgical portion of the study (pre-surgical cohort) and will receive pamiparib (BGB-290) 60 mg BID as a single agent for 7 days pre-surgery, including the day of surgery. At surgery fresh tumor tissue will be collected for correlative studies. Following recovery from surgery all patients will receive pamiparib (BGB-290) combined with TMZ post-operatively.

NCI # ABTC-1801

PI: [name]

Patients should begin presurgical treatment with pamiparib (BGB-290) starting 6 days (Day 1) prior to the day of scheduled tumor resection (Day 7). Two additional days of dosing are permitted if unexpected logistical problems delay the surgery.

Doses of pamiparib (BGB-290) should be taken 12 hours apart \pm 2 hours. On the day of surgery, the last pre-surgical dose must be taken 3-6 hours before surgery. The time that the dose is taken on the day of tumor resection must be recorded.

Blood samples for determining the concentration of drug in plasma will be collected from patients at baseline (prior to the first pre-surgical dose), on the day of surgery, immediately before the resection and immediately following the resection; see Section 9.5.2.

The tumor will be resected using neuronavigation or intraoperative MRI, enabling resection of enhancing tumor and resection or biopsy of non-enhancing tumor. Surgical resection of the non-enhancing lesions should be performed only in the non-eloquent areas that show FLAIR changes on MRI. Tissue may be collected from both the

ABTC # 1801

NCI # ABTC-1801

PI: [name]

enhancing core and non-enhancing edge of individual tumors. As a reminder, please refer to the Imaging Core Manual for further imaging requirements and submission information.

The concentration of pamiparib (BGB-290) will be determined in a $0.05-0.10 \text{ cm}^3$ (50-100 mg) section of tumor tissue obtained from a contrast enhancing and non-contrast enhancing region of the tumor. See Section 9.5.2.

Following surgery, all patients will continue with standard post-operative management.

Following recovery from surgical resection*, all patients will receive pamiparib (BGB-290) 60 mg BID in 28-day cycles combined with TMZ at the dose established in the Phase I portion (dose to be determined).

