- 13– Blood samples will be obtained for pharmacokinetics at baseline (prior to first pre-surgical dose), and shortly before and after surgical resection. Section 9.5.2.
- 14-Fresh tumor tissue for drug concentration will be collected day of surgery. See Sections 9.5.2.
- 15- Patient should be seen on the day of surgery (prior to surgery) to evaluate for AEs.
- 16– Within 3 days post-surgery.
- 17- Perform within minus 7 days of first dose.
- 18-± 1 day
- 19- In subjects whose CBC, Diff, Platelets have been stable through the first 6 cycles, the frequency of hematologic testing can be reduced to a q2 weeks schedule (Day 15 of every cycle and Pre-cycle evaluation) starting in Cycle 7. CBC, Diff, Platelets will be considered "stable" if the following criteria are met: 1) No reports of ANC<1500/µl in ANY of the Cycles 1-6 weekly Labs and 2) No reports of Platelets<100,000/µl in ANY of the Cycles 1-6 weekly Labs. If at any point during treatment on the revised q2 weeks schedule the above mentioned ANC and Platelets criteria are not met, CBC, Diff, Platelets should be repeated twice a week until counts are recovered (ANC ≥1500 or Platelets ≥100,000). Once counts are recovered, the schedule of CBC, Diff, Platelets should go back to, and stay at, weekly monitoring (NOT q2 weeks).

IMPORTANT: The guidance below is subject to applicable local Institutional Policy on telemedicine. In the event that local Institutional Policy regarding telemedicine differs from this guidance, then please follow local Institutional Policy.

Telemedicine visits may be substituted for in person clinical trial visits or portions of clinical trial visits where determined to be appropriate and where determined by the investigator not to increase the participants risks. Prior to initiating telemedicine for study visits the study team will explain to the participant, what a telemedicine visit entails and confirm that the study participant is in agreement and able to proceed with this method. Telemedicine acknowledgement will be obtained in accordance with the Guidance for Use of Telemedicine in Research. In the event telemedicine is not deemed feasible, the study visit will proceed as an in-person visit. Telemedicine visits will be conducted using HIPAA compliant method approved by the Health System and within licensing restrictions.

Additionally, informed consent should be obtained in person, but if deemed necessary, via telemedicine.

ABTC # 1801

NCI # ABTC-1801

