9.5.2 Brain Tissue Concentrations and Plasma Pharmacokinetics (Surgical Portion)

Tumor tissue pamiparib (BGB-290) levels, 2HG, and PARylation will be assessed in a patient subset treated with drug prior to re-resection (Surgical Portion), using optimized protocols in the Li group as noted in Section 9.5.1, and also based on methodology developed and validated in the [name] laboratory.

Blood samples for pharmacokinetics will be drawn at baseline (prior to first pre-surgical dose) and immediately before and after surgery. The PK sample drawn immediately before surgery must be taken following the Day 7 dose (which is taken 3-6 hours prior to surgery).

The concentration of pamiparib (BGB-290) will be determined in a 0.05-0.10 cm³ (50-100 mg) section of tumor tissue obtained from a contrast enhancing and non-contrast enhancing region of the tumor. Doses of pamiparib (BGB-290) should be taken at approximately the same time, in the morning, for 7 days (up to 9 days if surgery is delayed) with the last preoperative dose taken 3 to 6 hours prior to surgery.

Accurately record the time that the dose is taken prior to the tumor resection. The surgical procedure must be performed at least 3 hours but not longer than 8 hours after dosing. The biopsy specimens submitted for drug concentration determinations should be resected as close to 3-6 hours after dosing as possible, but not more than 8 hours after dosing.

Collection, preparation and shipping instructions for the frozen tissue specimens and the corresponding blood samples are provided in the study lab manual.

NCI # ABTC-1801

PI: [name]

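### The plasma PK analysis text for exploratory objective 7 plans non-compartmental Cmax, Cmin and AUC, but two post-dose samples per surgical patient cannot support them

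*Combined protocol and SAP*

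**What the plan says.** **Analysis.** In Section 11.0, exploratory objective 7 concerns tumor pamiparib, 2HG and PARylation in ten surgical patients. Its analysis text then turns to plasma. It gives the aim as steady-state pharmacokinetics at a given dose and sampling time, and continues: "Individual subject plasma concentration-time curves will be analyzed by non-compartmental methods using routines supplied in the WinNonlin" package. It closes: "Pharmacokinetic parameters, such as C_{max}, C_{min}, and AUC etc will be summarized descriptively".

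**Sampling.** Three places give the schedule.
- Section 4.3: a baseline draw before the first pre-surgical dose, then draws "on the day of surgery, immediately before the resection and immediately following the resection".
- Section 9.1.2, footnote 13: baseline, then "shortly before and after surgical resection".
- Section 9.5.2: "Blood samples for pharmacokinetics will be drawn at baseline (prior to first pre-surgical dose) and immediately before and after surgery".

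**Timing against the last dose.** Section 9.5.2 says: "The PK sample drawn immediately before surgery must be taken following the Day 7 dose (which is taken 3-6 hours prior to surgery". Sections 4.3 and 4.5.1 also put the last pre-surgical dose 3-6 h before surgery. Section 9.5.2 adds a wider limit for the operation itself: "The surgical procedure must be performed at least 3 hours but not longer than 8 hours after dosing". The time of the post-resection draw is not limited. Section 9.5.2 does ask sites to "Accurately record the time that the dose is taken prior to the tumor resection".

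**Other cohorts.** The Phase I and Phase II schedule in Section 9.1.1 has no PK row.

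**The concern.** A non-compartmental analysis works directly from the observed profile. Over a dosing interval it needs samples near the peak, a trough, and enough points between them to integrate. Here the only pre-dose sample is taken before any drug has been given, so it is not a steady-state trough. The two remaining samples are tied to the operation, not to the dosing interval.

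The plan therefore names an analysis that its own schedule does not feed. AUC would have to be left out, or built from imputed or extrapolated values. Any figures given as Cmax and Cmin would mix drug exposure with operating-room timing. Section 2.3 notes that the drug's penetration into human glioma is unknown, so plasma values from these ten patients may be read with interest.

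**Working it through.** The plan gives no figure to reproduce for this analysis, so the check has two parts: a count that needs no PK assumption, and an illustration that does.

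**1. Count and timing (Sections 4.3, 4.5.1, 9.1.1, 9.1.2, 9.5.2)**
- Draws per surgical patient: 3. Before any drug: 1. Post-dose: 3 - 1 = 2.
- Dosing interval: 12 h.
- First post-dose draw: about 3-6 h after the last dose, from the sentence in Section 9.5.2 that times this draw. Because surgery may fall up to 8 h after dosing, 8 h is a boundary case.
- Second post-dose draw: no stated limit.
- Share of the interval between the two draws, (t2 - t1)/12: draws at 3 and 8 h give 5/12 = 42%; 6 and 8 h give 2/12 = 17%; 3 and 12 h give 9/12 = 75%.

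In every case the first 3 h or more go unobserved. Two points also fit a terminal slope exactly, with 2 - 2 = 0 degrees of freedom left to check any extrapolation.

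**2. Illustration (assumed values)**

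Assumptions: one-compartment oral model at steady state; half-life 4, 8 or 16 h; ka 0.5, 1 or 2 per h; second draw at 8, 10 or 12 h. With ke = ln 2 / half-life,

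C(t) = ka/(ka - ke) × [exp(-ke t)/(1 - exp(-12 ke)) - exp(-ka t)/(1 - exp(-12 ka))].

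AUC over 12 h equals 1/ke in these units. The area between samples is the linear trapezoid (t2 - t1) × [C(t1) + C(t2)]/2.

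One case in full, half-life 4 h and ka 2 per h, where ke = 0.173, Cmax = 0.918 at 1.27 h, Cmin = 0.156 and AUC = 5.77:
- C(3) = 0.741, C(6) = 0.442, C(8) = 0.313.
- Higher value with first draw at 3 h: 0.741/0.918 = 81% of Cmax. With first draw at 6 h: 0.442/0.918 = 48%.
- Lower value with second draw at 8 h: 0.313/0.156 = 2.0 times Cmin.
- Area for draws at 6 and 8 h: 2 × (0.442 + 0.313)/2 = 0.755, and 0.755/5.77 = 13% of AUC.
- Same patient, first draw moved from 3 to 6 h: 0.741/0.442 = 1.68.

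Ranges over all nine combinations of half-life and ka:

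| First draw | Higher value / Cmax | Area between draws / AUC | C(3 h) / C(first draw) |
|---|---|---|---|
| 3 h | 81-100% | 43-73% | 1 |
| 6 h | 48-95% | 13-47% | 1.05-1.68 |
| 8 h (boundary) | 34-89% | 9-30% | 1.13-2.37 |

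(For the 8-h row the second draw is at 10 or 12 h.)

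With the first draw at 3 or 6 h, the lower value is 1.0-2.0 times Cmin. It reaches 1.0 only when the second draw is at 12 h. A short procedure with draws at 3 and 5 h gives 1.3-3.4 times Cmin.

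**The case against.** The strongest reply is that objective 7 itself asks for tumor drug level, 2HG and PARylation. Plasma Cmax, Cmin and AUC appear only in the analysis text, as examples. The stated aim, PK at a given dose and sampling time, can be met by two timed concentrations. This stands as a limit on scope. A reader might infer that objective 7 cannot be met, and the documents do not support that: the tissue analyses do not depend on the plasma profile. The reply does not rescue the sentences that name non-compartmental analysis and the three parameters.

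A second reply concerns size. A reader might take an 8-h first draw as the ordinary case and quote the shift of up to 2.37. The only sentence that times this draw ties it to a dose taken 3-6 h before surgery. The 8-h limit applies to the procedure and to the tissue specimens, which are taken after the draw. So 3-6 h is the main case and 8 h a boundary. Whether the two timing statements should be reconciled is a separate matter.

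A third reply is that the lab manual, which was not available, may say more. Section 9.5.2 refers to it for collection, preparation and shipping instructions. It may well cover draw times, but the protocol lists three draws and points to no others.

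A reader might also infer that a partial area will be published as AUC. Nothing in the documents shows that; AUC might simply be reported as not estimable.

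**Conclusion.** The point holds for the plasma PK analysis text only. With two post-dose samples, none in about the first 3 h and no steady-state trough, a non-compartmental AUC over 12 h cannot be obtained. The observed high and low are not reliable Cmax and Cmin, because both move with the time of surgery. This follows from the schedule alone and rests on no PK assumption.

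The size does rest on assumptions. Under slow absorption and slow elimination an early first draw can lie very close to Cmax, but the documents give no half-life or time to peak that would justify relying on this.

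The consequence is small: a descriptive, exploratory analysis in ten patients. It is worth correcting because the plan promises something the design cannot deliver and the correction is cheap.

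**What to change.** In the objective 7 analysis text of Section 11.0, replace the non-compartmental Cmax, Cmin and AUC analysis with observed plasma concentrations, listed per patient and summarised by actual time since dose for the pre-resection and post-resection draws. State that no interval parameters are derived. Use the recorded dose and draw times. The protocol already requires the dose time; confirm that the lab manual or case report form captures the draw times, and add a field if not.

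The cost is a wording change with no extra samples, plus that field if it is missing. The downside is giving up interval parameters that this sampling cannot support. Keeping them would need additional plasma draws and matching changes to Sections 4.3, 9.1.2 and 9.5.2.
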